3.1.1.2 Secondary Endpoints

- 1. Tolerance and adherence to diet assignment
- 2. Change in the following after 12 weeks of caloric restriction:
 - Visceral adiposity as measured by dual x-ray absorptiometry (DXA) and waist circumference
 - Fat and lean mass as measured by DXA
 - Hepatic steatosis and liver stiffness as measured by transient elastography
 - Lipid profile
 - REE as measured by indirect calorimetry
 - Serum biomarkers of inflammation (eg, CRP, TNF-alpha) and immune activation

4 Study Population

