6.4 Study Phase (Weeks 1-12)

Interim safety visits will be scheduled for weeks 1, 4, 8, and 12. Subjects will visit the NIH Clinical Center as outpatients. The following assessments and procedures will occur:

- 1. Vital signs including weight and blood pressure
- 2. Physical exam and interval medical history at weeks 4, 8, and 12
- 3. Fasting blood collection for acute care, hepatic, and mineral panels, insulin, glucose and lipids, and CRP, as well as serum, plasma, and PBMCs for storage at weeks 4, 8 and 12. Hgb A1C at week 12. Leptin, ghrelin, PYY, BDNF, inflammatory markers, urine ketones and HIV viral load will be repeated at weeks 4, 8, and 12.
- 4. Nutrition consultation at weeks 4 and 12: Completion of 3-day food diary and waist and hip measurements at weeks 4 and 12
- Review of subject diary documenting compliance and daily steps at weeks 1, 4,
 and 12

- 6. Symptoms Review Questionnaire at weeks 1, 4, 8 and 12
- 7. TFEQ at weeks 4, 8, and 12
- 8. Modified visual analog scales at week 12
- 9. At week 12, baseline assessments will be repeated. Assessments include:
 - Beck Depression Inventory, RAND SF-36, and PANAS questionnaires
 - REE
 - OGTT
 - DXA
 - Blood or urine pregnancy testing for women of childbearing potential
 - Transient elastography with CAP (Fibroscan®, Echosens, Paris, France)

Study visit windows are as follows: Week 1: +/-3 days, Weeks 4, 8, and 12: +/- 7 days.

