The TFEQ will be administered to measure three aspects of eating attitudes: cognitive restraint of eating, disinhibition, and hunger [50]. Modified visual analog scales (VAS) will be used to assess subjective hunger and satiety three times a day the days prior to week 0 and week 12 assessments [51, 52]. VAS assesses 'desire to eat,' 'hunger', 'fullness,' and 'prospective consumption.'.

PANAS

Subjects will report on Likert scales how they feel emotionally. The PANAS is a common index of emotional state [53].

Symptoms Review Questionnaire

Subjects will report on Likert scales their mood, level of energy, difficulty concentrating, headaches, feeling cold, constipation, negative emotions (depression, anxiety, irritability), hunger, and preoccupation with food for the week prior to the visit.

RAND SF-36 scale

This questionnaire gauges physical and psychosocial effects of the dietary interventions. It has been used as a quality of life assessment in previous studies of ICR [30].

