8.1 Potential Risks

Blood Draw. Collection of blood may be associated with discomfort, bruising, local hematoma formation and, on rare occasions, infections, lightheadedness, and fainting. The amount of blood drawn for research purposes will be within the limits allowed for adult subjects by the NIH CC (Medical Administrative Policy 95-9: Guidelines for Limits of Blood Drawn for Research Purposes in the Clinical Center: http://cc-internal.cc.nih.gov/policies/PDF/M95-9.pdf.

Pedometer. No risks are associated with pedometer use and it is associated with minimal inconvenience.

OGTT. No serious risks are associated with the OGTT. Some subjects experience temporary abdominal discomfort after drinking the sugar solution. If the results of an OGTT demonstrate glucose intolerance or insulin resistance, recommendations will be made for appropriate follow-up monitoring and management.

REE. Subjects may experience claustrophobia during the measurements.

Transient elastography. There are no foreseeable risks associated with this non-invasive procedure.

DXA. Subjects will be exposed to radiation from three DXA scans, for total estimated effective dose in 1 year of 0.00007 rem. This is considered a low exposure. The risk of this exposure is too low to be reliably measured.

Caloric restriction. [29, 30, 57, 58] In previous studies of ICR, no serious adverse events (SAEs) occurred. In the study by Harvie et al., a 6-month trial, 8% of subjects on the 2-5 ICR regimen reported physical symptoms including lack of energy, headaches, feeling cold, and constipation. Minor psychological symptoms were reported in 15% of the 2-5 ICR group, including lack of concentration, bad temper, and a preoccupation with food. These adverse effects abated after caloric restriction was stopped [29, 30]. Conversely, 6% of 2-5 ICR subjects reported better health and increased energy [30]. Furthermore, 32% of 2-5 ICR had increased self-confidence and positive mood. Overall, a minority of subjects (9-15%) would be expected to develop minor physical and psychological AEs related to 2-5 ICR. Such AEs include lethargy, feeling cold, difficulty concentrating, and irritability. Study subjects will be counseled on potential side effects and will record symptoms in the diet and symptom diary.

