12.1 Overview and Design

This is a randomized controlled, study of 12 weeks of ICR versus standard of care. Changes from baseline to 12 weeks in measures of the primary endpoints (weight and insulin sensitivity) and secondary endpoints (eg, hepatic fat content, inflammatory biomarkers) will be compared between the 2 study arms. The 12-week follow-up period after the randomized portion of the study is designed to monitor changes in weight and metabolic parameters after completion of the 2-5 ICR diet arm and the standard-of-care arm.

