12.4 Description of the Analyses

For the primary endpoint, the between group effect on weight will be tested using a two-sided t-test (p-value <0.05) of the calculated change in weight from baseline to 12 weeks. This will be conducted using on-treatment data, ie, data from all randomized subjects who completed baseline and 12 weeks evaluations regardless of reported compliance. Similarly, between group differences in insulin resistance measured by HOMA-IR will be determined. A secondary analysis will use analysis of covariance to adjust for the baseline value of the given endpoint.

In the analyses of the secondary endpoints (eg, visceral adiposity, serum lipids, markers of inflammation, hepatic fat content results), two-sided t-test comparing change from baseline to 12 weeks will be calculated between groups. In addition, within group paired t-tests may be performed to determine if, during the 12 week follow up if any of the changes during the randomized intervention portion of the study are sustained after 12 weeks of no intervention.

13 Ethics/Protection of Human Subjects

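### The one between-arm rule for secondary endpoints, change from baseline to week 12, leaves the week 1, 4 and 8 symptom scores out of any planned comparison of tolerance

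*Combined protocol and SAP*

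**What the plan says.** Section 2.2 makes tolerability of intermittent caloric restriction (ICR) a secondary objective. Section 3.1.1.2 lists "Tolerance and adherence to diet assignment" as the first secondary endpoint, without naming an instrument, a time point or a summary measure. The second item in that list is a set of measures whose change after 12 weeks is of interest.

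Section 6.4 schedules the "Symptoms Review Questionnaire at weeks 1, 4, 8 and 12"; Section 6.2 adds a baseline questionnaire and Section 6.5 one at week 24. Section 7 describes Likert items on mood, energy, concentration, headache, feeling cold, constipation, negative emotions, "hunger, and preoccupation with food for the week prior to the visit". These largely match the side effects that Section 8.1 reports from an earlier 6-month trial.

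On analysis, Section 12.1 says that "Changes from baseline to 12 weeks in measures of the primary endpoints (weight and insulin sensitivity) and secondary endpoints" will be compared between arms. Section 12.4 repeats this for secondary endpoints as a "two-sided t-test comparing change from baseline to 12 weeks will be calculated between groups". Beyond that it offers only that "within group paired t-tests may be performed to determine if, during the 12 week follow up" changes are sustained; these tests are optional, within arm, and about the period after the diet.

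**The concern.** A single end-of-diet value is a natural summary for weight, fat mass or lipids, where the state reached is the question. Tolerance is about what subjects experienced throughout the 12 weeks. With one-week recall, a symptom present at week 1, 4 or 8 but absent in the last week before the week-12 visit does not enter a week-12 change.

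Two things are at stake. First, the planned comparison could miss a difference between arms that occurred earlier in the diet, in a trial whose précis hypothesises that the diet is acceptable. Second, whatever the time course, three of the four on-diet measurements are collected and then left out, so the estimate is less precise than the data allow. If no rule is fixed in advance, the choice of visit and summary would also be made after the scores are known.

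**Working it through.** **Step 1. Trace each symptom score to an analysis.**

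| Questionnaire | Scheduled in | Between-arm use in Section 12 |
|---|---|---|
| Baseline | 6.2 | Reference for the week-12 change |
| Weeks 1, 4, 8 | 6.4 | None |
| Week 12 | 6.4 | Change from baseline, if the rule covers tolerance |
| Week 24 | 6.5 | None (optional within-arm tests only) |

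The analysis of covariance in 12.4 adjusts for the baseline value; it brings in no further visits. Section 12 contains no adverse event table or comparison.

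**Step 2. Precision, with no fading assumed.** The documents give no variance or correlation for the symptom scores. Assume the same variance at every visit (set to 1) and the same correlation ρ between any two visits.

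- Week-12 change: variance = 1 + 1 − 2ρ = 2(1 − ρ).
- Mean of four on-diet scores minus baseline: variance = (1 + 3ρ)/4 + 1 − 2ρ = 1.25(1 − ρ).
- Ratio of variances = 1.25/2 = 0.625. Ratio of standard errors = √0.625 = 0.79, a 21% reduction. ρ cancels, so the result is the same at 0.3, 0.5 or 0.7.

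Because 1/0.625 = 1.6, 25 subjects per arm with the four-visit mean give the precision of 40 per arm with week 12 alone.

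In SD units at ρ = 0.5:

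| Per arm | SE, week 12: √(2/n × 1) | SE, four-visit mean: √(2/n × 0.625) | 95% CI half-widths |
|---|---|---|---|
| 25 | 0.283 | 0.224 | 0.57 and 0.45 |
| 17 (dropout case in 12.3) | 0.343 | 0.271 | 0.70 and 0.55 |

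The half-widths use t = 2.01 (48 df) and 2.04 (32 df).

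**Step 3. The same with baseline adjustment.** The variances become 1 − ρ² for week 12 and (1 + 3ρ)/4 − ρ² for the mean. At ρ = 0.5 these are 0.75 and 0.375, an SE ratio of √0.5 = 0.71. At ρ = 0.3 the ratio is √(0.385/0.91) = 0.65, and at ρ = 0.7 it is √(0.285/0.51) = 0.75. The averaging gain is therefore at least as large in the adjusted analysis.

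**Step 4. What averaging cannot do.** An effect of 0.8 SD at week 1 only becomes 0.8/4 = 0.2 SD in the mean. With 25 per arm and ρ = 0.5, power for that is 14%. A brief early effect therefore needs the visit-by-visit table as well as the mean.

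**The case against.** The strongest reply is that the week-12 rule was never meant for tolerance. Section 3.1.1.2 lists tolerance apart from the change measures, and the examples in 12.4 (visceral adiposity, lipids, inflammation markers, hepatic fat) all come from the second group. The hypotheses in 12.2 do not mention tolerance either, and descriptive reporting would meet the objective. This is a fair reading, but it leaves a named secondary endpoint with no measure and no analysis, so text is needed on either reading.

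Second, early symptoms are not lost. Section 11.2 elicits adverse events at each contact and counts survey tools among source documents; 11.6 follows events from enrolment; 11.8 keeps replaced subjects in the safety assessments. This stands. However, only reportable events go into the study database, and Section 12 neither defines those safety assessments nor plans a summary by arm.

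A reader might go further and infer that the plan will report known side effects as absent. The documents do not support that. "Minor psychological symptoms were reported in 15% of the 2-5 ICR group" in the cited trial, and Section 8.1 says these effects abated once restriction stopped; nothing says they fade while the diet continues. At a 15% rate, the chance of no affected subject among 25 is (1 − 0.15)^25 = 1.7%. It rises at week 12 only if a share of affected subjects is assumed to have recovered by then: 5%, 14% or 39% if 75%, 50% or 25% remain symptomatic. If symptoms persist, it does not rise. These counts also differ in kind from a comparison of mean Likert scores, and they carry a 6-month rate over to 12 weeks.

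Nor would a large gain in power follow. For a 15% rate to produce a mean shift of 0.8 SD, each affected subject would have to shift by 0.8/0.15 = 5.3 SD. A constant 2-SD shift in 15% of subjects gives a mean shift of 0.3 SD and, at ρ = 0.5 with 25 per arm, power of 18% at week 12 and 26% with the four-visit mean. This argues for an estimate with an interval rather than a test.

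**Conclusion.** The point holds as a gap in the analysis of tolerance. Under the stated rule, one of four on-diet questionnaires is compared between arms; under the narrower reading, none is. That part rests on the text alone. A missed early effect is possible, and its likelihood cannot be sized from the documents.

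The size that can be defended is the 21% smaller standard error of the between-arm change. It assumes equal variances, equal correlations and complete questionnaires; a correlation that weakens with time between visits would alter the figure. It does not depend on symptoms fading.

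The change is worth making before scores are examined by arm. It leaves the weight and HOMA-IR analyses untouched, and it is a matter of analysis only: nothing here concerns the diet, its stopping or other clinical management.

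**What to change.** State in 12.1 and 12.4 that tolerance is not limited to the baseline-to-week-12 change, and add to 12.4:

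- Each Symptoms Review item will be compared between arms as the mean of the available on-diet scores (weeks 1, 4, 8 and 12), adjusted for baseline, and reported as an estimate with a 95% CI.
- All randomised subjects with at least one on-diet questionnaire will be included.
- Scores will be tabulated by arm at every visit, including weeks 1, 12 and 24, so that a brief early effect is not diluted by the average.

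A tempting addition is the proportion of subjects whose worst on-diet score is worse than baseline. As an absolute figure it misleads. With five exchangeable continuous scores and no diet effect, baseline is the highest only one time in five, so 80% of both arms would qualify by chance. Leave it out, or report it only as a between-arm difference with a pre-set worsening threshold and a note on this chance effect.

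The cost is a few sentences and a little more analysis, with no new visit, questionnaire or procedure. The downside is that the average does not isolate the state at week 12, which is why the week-12 scores stay in the table. For subjects who leave early, the mean covers fewer visits; the numbers contributing at each visit should be shown.

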3.1 Description of the Study Design

After completing screening procedures and establishing eligibility, all subjects will receive standard-of-care recommendations for healthy diet and lifestyle and will be randomized 1:1 to either 2 days of ICR per week with 5 days of ad lib eating (2-5 ICR) or no additional intervention (see below).

Standard of Care (n=25)	2-5 ICR (n=25)
 AHA dietary counselling Lifestyle and physical activity counselling Pedometer and instructions for use 	 AHA dietary counselling Lifestyle and physical activity counselling Pedometer and instructions for use
	ICR guidelines and instructionsSupplemental beverages for ICR days

All subjects will receive dietary counseling consistent with the American Heart Association (AHA) diet recommendations. Like the standard-of-care arm, the 2-5 ICR subjects will implement the AHA diet 5 days per week; however, on 2 days per week will consume approximately 25% of their estimated daily caloric needs in the form of supplemental beverages or small meals. Assessments will occur prior to randomization and at 1, 4, 8, and 12 weeks. All subjects will then complete a follow-up visit to assess changes in weight and metabolic parameters 12 weeks after the intervention period is complete.

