6.5 Final Follow-up Visit (Week 24)

After completing the 12-week randomized portion of the study, subjects will be followed for an additional 12 weeks during which time they will not be instructed to follow any specific dietary pattern. Both groups' visits will occur at week 24. (+/- 4 weeks)

The following procedures will be performed:

- 1. Vital signs including weight and blood pressure
- 2. Physical exam and interval medical history
- 3. Fasting blood collection for acute care, hepatic, and mineral panels, Hgb A1C, insulin, glucose and lipids, as well as serum, plasma, PBMCs for storage
- 4. Symptoms Review Questionnaire
- 5. Modified visual analogue scale
- 6. Transient elastography with CAP
- 7. 3-day food diary and anthropometric measurements
- 8. REE
- 9. DXA scan
- 10. Blood or urine pregnancy testing for women of childbearing potential

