11.8 Replacement of a Subject Who Discontinues Study Treatment

If a subject withdraws after fewer than 12 weeks on study diet assignment, then they will be replaced. If a subject is replaced, their data will still be included for the safety assessments.

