12.3 Sample Size Justification

Using an alternate day fasting strategy for weight loss in obese adults (n=13), Catenacci et al [57] observed that subjects lost 8.2±0.9 kg (mean ± standard error of the mean) after 8 weeks. For sample size justification, we will use a conservative estimate of 8-kg weight loss after 12 weeks with ICR, and assume 4-kg weight loss among the observation group due to monitoring and counselling through study visits. Therefore, using the standard deviation estimate from Catenacci et al. of 3.24, we will have 96.7% power to detect a 4-kg difference in weight loss between treatment arms with 25 subjects in each arm. With 17 subjects per arm (ie, approximately a 30% dropout rate), the power will be 93.7% to detect a 4-kg difference in weight loss.

In previous studies of ICR, HOMA-IR improvements ranged from 9% to 30%, depending on a number of factors, including the duration of the study, extent and timing of caloric restriction, and whether or not meals were provided [59]. Assuming a baseline HOMA-IR of 1.5, a standard deviation of change in HOMA-IR of 0.25, a study size of

25 subjects per arm, we will have >80% power to detect the difference between a 25% improvement in insulin sensitivity with ICR versus a 10% improvement in the observation arm as measured by HOMA-IR. The power to detect this difference will be 72.1% with 17 subjects per arm.

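### Week 24 has only optional within-arm paired t-tests and no between-arm estimate, although both randomised arms are measured then

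*Combined protocol and SAP*

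**What the plan says.** Section 12.1 sets the comparison between arms as "Changes from baseline to 12 weeks in measures of the primary endpoints (weight and insulin sensitivity) and secondary endpoints". Section 12.4 agrees: the t-tests for weight and HOMA-IR, and those for the secondary endpoints, are all of change to week 12. The secondary ANCOVA adjusts each endpoint for its baseline value, and section 3.1.1 defines the endpoints that carry a time point as 12-week changes.

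For the later period, section 12.1 says that the follow-up is "designed to monitor changes in weight and metabolic parameters after completion of the 2-5 ICR diet arm and the standard-of-care arm", without naming a comparison. Section 12.4 adds that "within group paired t-tests may be performed to determine if, during the 12 week follow up if any of the changes" seen in the randomised phase last through 12 weeks without intervention. It does not say whether the pairing is week 12 with week 24 or baseline with week 24, or what result would count as sustained.

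The data cover both arms. Section 3.1 states: "All subjects will then complete a follow-up visit to assess changes in weight and metabolic parameters 12 weeks after the intervention period is complete". Section 6.5 lists weight, fasting insulin, glucose and lipids, anthropometrics, elastography with CAP, REE and DXA at that visit.

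**The concern.** The arms share the AHA dietary counselling, activity counselling and pedometer (section 3.1), and section 12.3 is explicit that the control arm should lose weight too: "assume 4-kg weight loss among the observation group due to monitoring and counselling through study visits". If the ICR arm holds its loss at week 24, a paired test in that arm cannot tell an effect of ICR from what counselling and study visits alone would have produced. The randomised contrast that could tell them apart is available from planned measurements, but no analysis of it is specified.

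Two further weaknesses follow from the wording. If the pairing is week 12 with week 24, a non-significant result is absence of evidence for regain and not evidence of maintenance. And paired tests run separately in each arm invite the reader to compare one p-value with the other, which is not a test of the difference between arms. Because the tests are optional, the choice of what to report at week 24 could also be made after seeing the data.

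At stake is any statement that the effect of ICR lasted after the diet stopped.

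**Working it through.** **1. Is a week-24 comparison between arms planned anywhere?** The objectives (2.1, 2.2), endpoints (3.1.1), hypotheses (12.2), overview (12.1) and analyses (12.4) were read together. Where a time point is given for a comparison between arms, it is week 12. The hypotheses compare the arms but name no time point. No week-24 contrast appears.

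**2. Inputs.** Two-sided 5% level (12.4); 25 per arm, or 17 after about 30% dropout (12.3); SD of weight change 3.24 kg (12.3). The documents give no SD for any week-24 change. SD 5 kg is an assumption to show the range. A 2-kg change is an illustration, half the 4-kg planning difference.

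**3. The plan's own figures.** There is no week-24 figure to reproduce. As a check of method, two-sample noncentral-t power for 4 kg at SD 3.24 has noncentrality 4/(3.24 × √(2/n)).
- n = 17: 3.60, power 93.7%, as stated in 12.3.
- n = 25: 4.36, power 99.0%, against 96.7% stated. The plan's figure understates power. That is a separate matter and does not bear on this point.

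**4. Within-arm test, week 12 to week 24, true regain 2 kg.** Noncentrality is 2/(SD/√n). The chance of missing the regain is 1 − power. The 95% CI half-width is t(0.975, n−1) × SD/√n, with t = 2.064 (n = 25) or 2.120 (n = 17).

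| SD (kg) | n | noncentrality | regain missed | CI half-width (kg) |
|---|---|---|---|---|
| 3.24 | 25 | 3.09 | 15.8% | 1.34 |
| 3.24 | 17 | 2.55 | 33.3% | 1.67 |
| 5 | 25 | 2.00 | 51.6% | 2.06 |
| 5 | 17 | 1.65 | 65.9% | 2.57 |

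**5. Comparing two within-arm p-values.** Suppose both arms have the same true week 12–24 change and SD 3.24. If each arm's test has power p, exactly one is significant with probability 2p(1−p).
- 25 per arm: 1 kg, p = 0.317, so 43%; 1.5 kg, p = 0.603, so 48%.
- 17 per arm: 1 kg, p = 0.224, so 35%; 1.5 kg, p = 0.434, so 49%.

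So a seeming difference in durability would often appear where none exists.

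**6. What a between-arm estimate would give.** For unadjusted change, the half-width is t(0.975, 2n−2) × SD × √(2/n), with t = 2.011 (25 per arm) or 2.037 (17 per arm). Power is for a true remaining difference of 2 kg.

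| SD (kg) | n per arm | CI half-width (kg) | power for 2 kg |
|---|---|---|---|
| 3.24 | 25 | 1.84 | 57% |
| 3.24 | 17 | 2.26 | 42% |
| 5 | 25 | 2.84 | 28% |
| 5 | 17 | 3.49 | 20% |

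For HOMA-IR, the plan's SD of change of 0.25 gives half-widths of 0.14 and 0.18.

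**7. Timing.** Section 6.4: "Study visit windows are as follows: Week 1: +/-3 days, Weeks 4, 8, and 12: +/- 7 days". Section 6.5: "visits will occur at week 24. (+/- 4 weeks". The shortest interval between the two visits is (24 − 4) − (12 + 1) = 7 weeks; the longest is (24 + 4) − (12 − 1) = 17 weeks. Table 2 in section 7 carries different window entries for these visits, so the interval rests on sections 6.4 and 6.5.

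**The case against.** The best defence is that the plan asks a modest question and names a method that suits it. Whether a change persists after the diet stops is a within-person question, the study is a pilot, the follow-up is described as monitoring, and durability is not an objective, endpoint or timed hypothesis. Paired tests in both arms would also put the control arm's change beside the ICR arm's, and the optional wording does not forbid a formal contrast. This stands as far as weight goes: nothing confirmatory depends on week 24. It does not remove the gap. Placing two within-arm results side by side is not an estimate of their difference, and step 5 shows how misleading it can be.

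A second objection is that the missed-regain rates hold only for a week 12 versus week 24 pairing. With baseline versus week 24, a significant result would support a retained change and those rates would not apply. That is correct, and the plan does not say how a non-significant result would be read. The rates are therefore conditional. The attribution problem is the same under either pairing.

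Third, the proposed contrast is imprecise, and the data set would consist of completers, because section 11.8 says: "If a subject withdraws after fewer than 12 weeks on study diet assignment, then they will be replaced". Both points are true. The completer set and the wide visit windows limit the paired tests equally, and low precision is a reason to report an estimate with its interval, not a reason to leave it out.

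**Conclusion.** The concern holds. The plan collects a randomised comparison at week 24 and specifies no analysis of it. The one method named is optional, leaves its pairing and its criterion open, and cannot separate an ICR effect from the effect of counselling. The consequence is confined to the exploratory conclusion about durability; the week-12 primary and secondary analyses are untouched. The change should be made because it is cheap.

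The missed-regain range of 16% to 66% assumes a week 12 versus week 24 pairing, a 2-kg regain, SDs of 3.24 or 5 kg, and a reading of non-significance as maintenance that the plan does not state. The text-based finding needs none of these assumptions.

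**What to change.** Replace the last sentence of section 12.4 with wording such as:

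> At week 24, weight, HOMA-IR, waist circumference, DXA measures, CAP, liver stiffness, lipids and REE will be compared between arms as randomised by ANCOVA adjusted for the baseline value, in subjects with baseline and week-24 data. These comparisons are exploratory and will be reported as estimate and 95% CI, with the numbers missing and replaced in each arm and the observed range of weeks since the week-12 visit. Within-arm changes from week 12 to week 24 and from baseline to week 24 will be described with 95% CIs. Non-significance will not be taken as evidence that a change is sustained.

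Baseline-adjusted ANCOVA is already the secondary analysis in section 12.4. The list follows section 6.5, which does not include CRP or inflammatory markers at week 24 (only stored serum and plasma).

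The cost is four sentences and no new data. The drawbacks are a few more exploratory comparisons and the limited precision shown in step 6, so the result would inform the durability question without settling it. The completer set and the 7-to-17-week spacing remain, which is why the wording asks for both to be reported.

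### The optional within-group paired t-tests in Section 12.4 cannot show whether week-12 changes are sustained at week 24, whichever time points are paired

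*Combined protocol and SAP*

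**What the plan says.** Section 12.1 gives the purpose of the second 12 weeks: the period "is designed to monitor changes in weight and metabolic parameters after completion of the 2-5 ICR diet arm" and after the standard-of-care arm. Section 6.5 brings both arms back at week 24 for weight, fasting bloods, DXA, resting energy expenditure and elastography.

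The only analysis that Section 12 plans for these data is one optional sentence in Section 12.4: "within group paired t-tests may be performed to determine if, during the 12 week follow up if any of the changes" made during the randomized part of the "study are sustained after 12 weeks of no intervention". It does not name the two time points to be paired, define sustained, set a retained amount, or ask for a confidence interval. The between-arm tests in the same section cover baseline to week 12 only.

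**The concern.** The sentence names a method and the conclusion that the method is meant to deliver, and the two do not match.

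- If week 24 is paired with week 12, the natural reading is that a non-significant change means sustained. Failing to reject is not evidence of no regain, and fewer week-24 attenders make that outcome more likely.
- If week 24 is paired with baseline, the natural reading is that a significant change means sustained. That test shows only that some change remains, not how much of the week-12 change was kept.

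At stake is what the trial says about durability after the diet stops. Because the pairing is open, it could also be chosen after the data are seen.

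**Working it through.** **Inputs (Section 12.3 unless stated)**
- Weight loss at week 12: 8 kg with intermittent restriction ("we will use a conservative estimate of 8-kg weight loss after 12 weeks with ICR") and 4 kg with standard of care ("assume 4-kg weight loss among the observation group due to monitoring and counselling through study visits").
- SD of weight change: 3.24 kg, from an 8-week standard error of 0.9 in 13 people (0.9 × √13 = 3.245).
- HOMA-IR: baseline 1.5, SD of change 0.25. Planned gains are 25% × 1.5 = 0.375 and 10% × 1.5 = 0.15.
- n per arm: 25, or 17 after dropout.
- Two-sided 0.05. Section 12.4 states this for the primary weight test ("tested using a two-sided t-test (p-value <0.05) of the calculated change in weight from baseline to 12 weeks"); it is assumed for the paired tests.
- The plan gives no SD for change to week 24. The week-12 SDs are carried over as an assumption, with 2 to 5 kg as the range for weight.

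**The plan's own figures.** None is given for week 24. As a check on the inputs, two-sample t-test power (noncentral t) at 17 per arm is 93.7% for weight and 72.1% for HOMA-IR, both as stated. The stated 96.7% for weight at 25 per arm does not reproduce: the result is 99.0%, and 96.7% corresponds to 20 per arm. That is a separate matter and nothing below uses it.

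**Formulas.** Smallest significant mean = t(0.975, n−1) × SD/√n. Power is from the noncentral t with n−1 degrees of freedom and noncentrality δ/(SD/√n).

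**Pairing 1: baseline with week 24, intermittent-restriction weight.** At SD 3.24, n=25: 2.064 × 3.24/5 = 1.34 kg. At n=17: 2.120 × 3.24/4.123 = 1.67 kg. Share that can be regained: (8 − 1.34)/8 = 83% and (8 − 1.67)/8 = 79%. For a true residual of 2 kg, noncentrality is 2/0.648 = 3.09 and 2/0.786 = 2.55.

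| SD (kg) | n | Smallest significant mean loss (kg) | Share of 8 kg regained at that point | Chance of significance, true residual 2 kg |
|---|---|---|---|---|
| 2 | 25 | 0.83 | 90% | 99.8% |
| 2 | 17 | 1.03 | 87% | 97.2% |
| 3.24 | 25 | 1.34 | 83% | 84.2% |
| 3.24 | 17 | 1.67 | 79% | 66.7% |
| 5 | 25 | 2.06 | 74% | 48.4% |
| 5 | 17 | 2.57 | 68% | 34.1% |

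**Pairing 2: week 12 with week 24.** Chance that a true loss of effect is non-significant (1 − power):

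| True loss of the week-12 change | SD | n=25 | n=17 |
|---|---|---|---|
| Restriction weight, half (4 of 8 kg) | 3.24 | under 0.1% | 0.3% |
| Restriction weight, half (4 of 8 kg) | 5 | 3% | 13% |
| Standard-of-care weight, half (2 of 4 kg) | 3.24 | 16% | 33% |
| Restriction HOMA-IR, half (0.1875 of 0.375) | 0.25 | 5% | 17% |
| Standard-of-care HOMA-IR, all (0.15) | 0.25 | 18% | 36% |

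**The pairings can disagree on the same data.** If 4 of 8 kg is regained, 4 kg remains. At SD 3.24 each test then has power above 99% at either n. One pairing points to not sustained and the other to sustained.

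**The case against.** The case against has four parts.

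- **The tests are optional and no rule is written.** Section 12.4 nowhere says that a p-value above or below 0.05 means sustained. A reader might infer that the plan commits to such a rule; it does not. This stands. But the sentence does say that the tests are there to determine whether changes are sustained, and Section 12 offers no other week-24 analysis.
- **Persistence is not an objective, endpoint or hypothesis** (Sections 2, 3.1.1 and 12.2), and the précis calls the study a pilot. This stands and limits the reach of the point.
- **Large weight regain in the restriction arm would be detected.** A reader might infer that the week 12 to 24 test would often overlook loss of most of the benefit. For that arm's weight the documents' figures do not support this: a 4-kg regain is almost never missed at SD 3.24. Failure to detect is a problem mainly for HOMA-IR and the standard-of-care arm.
- **The week-24 SD and n are uncertain.** At SD 5 kg, a 2-kg residual is significant in about half of trials or fewer. Section 11.8 replaces subjects who withdraw before 12 weeks, so 17 at week 24 is an assumption about later loss. Both points stand, and the results are therefore shown as ranges.

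A paired t-test does come with a mean change and an interval, and nothing forbids reporting them. The plan does not ask for them or base the conclusion on them.

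**Conclusion.** The point holds as one about inference. Under neither pairing does a paired significance test establish that a change was sustained, and the pairing itself is not fixed. The baseline pairing is the more permissive: at the carried-over SD of 3.24 kg, about 80% of the planned 8-kg loss can be regained with the test still significant. The week 12 to 24 pairing is weak for small planned changes and adequate for a 4-kg weight regain in the restriction arm.

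The sizes rest on three assumptions: week-12 SDs applied to changes ending at week 24, two-sided 0.05, and 17 to 25 subjects per arm. A reader might infer that the trial's main results are compromised. They are not: the primary and secondary comparisons run from baseline to week 12 and do not depend on this sentence.

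**What to change.** In Section 12.4, replace the test-based verdict with estimation. For each arm, report the mean week 12 to week 24 change and the mean baseline to week 24 change, each with a 95% confidence interval, beside the baseline to week 12 change. State that persistence will be described from these intervals and not inferred from a significant or non-significant p-value. If the word sustained is to be used, state before week-24 data are examined the largest loss of effect compatible with it, and require the interval to exclude that loss.

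This takes a few sentences and no new data. At SD 3.24 kg the interval for weight change is ±1.34 kg (n=25) or ±1.67 kg (n=17). The cost is that some results will be inconclusive, above all in the standard-of-care arm. If, for illustration, the limit were half of that arm's planned HOMA-IR gain (0.15/2 = 0.075), the interval would exclude it in only 30% (n=25) or 21% (n=17) of trials even with no true loss. A ratio for the share retained is best avoided, because it is unstable when the week-12 change is small.
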